# 13.1.2 Pharmacokinetic Urine Sampling

Urine samples will be collected according to the time schedule presented in Appendix 2.

A pre-dose (blank) urine sample will be taken at least 1 h before dosing. All individual urine voids will be collected and pooled per collection period. The pooled sample will be weighed, the volume will be calculated and an aliquot of urine for each collection period will be shipped to the bioanalytical laboratory for analysis, according to Quotient Sciences SOPs, unless indicated otherwise by the sponsor.

Samples will be collected into appropriate containers containing bovine serum albumin and shipped as specified by the bioanalytical laboratory. Details of sample containers and processing will be contained in the Clinical Sample Processing Manual.

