#### 7.2.3 Exploratory Endpoints

- Changes in clinical early renal toxicity markers in urine: alpha-glutathione Stransferase (α-GST), clusterin (CLU), Cystatin C (CysC), Kidney Injury Molecule-1 (KIM-1), neutrophil gelatinase-associated lipocalin (NGAL), osteopontin (OPN), albumin (ALB) and total protein (TPRO).
- Identification of DNDI-0690 metabolite profile (to be reported separately)
- Analysis of Holter extracted ECGs for the following parameters: RR, heart rate (HR), PR, QRS, QT, corrected QT interval by Fridericia's formula (QTcF), corrected QT interval by Bazett's formula (QTcB), ΔHR, ΔRR, ΔPR, ΔQRS, ΔQT, ΔQTcF and ΔQTcB.
- Comparison of the PK parameters AUC(0-t), AUC(0-inf) and Cmax of DNDI-0690 in the fed state versus fasted state in male subjects
- Comparison of the PK parameters AUC(0-t), AUC(0-inf) and Cmax of DNDI-0690 in WONCBP subjects versus male subjects

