#### 13.3.2 Urine Sampling for Drug-related Renal Injury Exploratory Biomarkers

Urine samples for drug-related renal injury exploratory biomarkers will be collected according to the time schedule presented in Appendix 2.

Samples will be taken as an aliquot from PK urine collection after the sample has been weighed. Urine samples will be collected and processed as detailed in the Clinical Sample Processing Manual.

Samples will be stored and may be analysed at the end of the trial retrospectively or as required during the study if medically relevant changes in the renal parameters of safety laboratory assessments are observed (ie, BUN, creatinine):

- α-GST
- CLU
- CysC
- KIM-1
- NGAL

- OPN
- ALB
- TPRO

The samples will be stored until finalisation of the clinical study report, and destroyed if no analyses are to be performed.

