# 14.6.2 Urinalysis

Urinalysis will be performed on-site using a dipstick according to the time schedule presented in Appendix 2. Urine samples will be collected and processed as detailed in the Clinical Sample Processing Manual. Any urine used for urinalysis will be added back to the full sample for PK analysis. If microscopy is required, a urine sample (approximately 20 mL) will be taken from the urine PK collection, after the sample has been weighed and sent to The Doctors Laboratory.

The acceptable deviations from the nominal urine sampling time points for urinalysis are:

• Post-dose urine samples will be taken ± 2 h from the nominal urine sampling time

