Haematology, coagulation and clinical chemistry, LDH, BUN, Uric acid, GLDH, Cholesterol and Cystatin C at each time point. Virology at screening only. Creatinine clearance will be estimated at screening for eligibility purposes and at each time point, from serum creatinine using the Cockcroft-Gault equation.

h Time points may be altered based on emerging data from previous cohorts, see Section 8.2.1.

Post-menopausal female subjects only

 Holter monitoring will begin at least 1 h prior to dosing and end 24 h post-dose after last PK time point. All ECG extractions will be taken in triplicate. Three sets of triplicate ECG extractions to be taken at pre-dose (for baseline). Holter extraction time points on Day 1 will be: pre-dose and 0.5, 1, 1.5, 2, 2.5, 3, 4, 6, 9, 12 and 24 h post-dose.

k ECGs to be taken in triplicate at pre-dose (for baseline), all post-dose time points single ECG. An ECG can be repeated for any reason (technical in particular). The Principal Investigator or sub-investigator must double-check the results.

Blood pressure and HR at every time point. Tympanic temperature at screening and pre-dose only.

m Urine will be collected for DNDI-0690 at the following intervals: Pre-dose, 0-12, 12-24, 24-48, 48–72 h post-dose. See Section 13.1.2 for more details.

n Urine samples for exploratory biomarkers for drug-related injury will be taken as an aliquot from PK urine collection at Pre-dose, 12, 24, 48 and 72 h post-dose. See Section 13.3.2 for details.

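### As worded, the renal-injury biomarker aliquots come from PK urine collected into bovine serum albumin, so urinary total protein, and possibly albumin, could not be interpreted

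*Protocol*

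**What the plan says.** Three places in the protocol fix the path of the sample.

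- **Section 13.1.2 (PK urine).** "All individual urine voids will be collected and pooled per collection period". The pool is weighed and an aliquot for each period goes to the bioanalytical laboratory. The section then says: "Samples will be collected into appropriate containers containing bovine serum albumin", and the same sentence goes on to shipment on that laboratory's terms.
- **Section 13.3.2 (renal-injury biomarkers).** "Samples will be taken as an aliquot from PK urine collection after the sample has been weighed". The aliquots are stored. They may be assayed retrospectively, or during the study if relevant changes appear in the renal safety laboratory values.
- **Appendix 2, footnote n.** The biomarker samples "will be taken as an aliquot from PK urine collection at Pre-dose, 12, 24, 48 and 72 h post-dose".

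The eight urine markers in Section 7.2.3 include "albumin (ALB) and total protein (TPRO"). The protocol describes no additive-free container, no aliquot taken before contact with the additive, no correction for added protein and no requirement on assay specificity. Sections 13.1.2 and 13.3.2 leave further handling detail to the Clinical Sample Processing Manual. Section 15.4 adds that the urinary biomarker data will not be analysed as part of this study at this stage.

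**The concern.** Bovine serum albumin is itself a protein. If it is already in the urine when the biomarker aliquot is taken, a total-protein assay reads it together with anything the kidney has leaked. An albumin assay reads it too, unless it is specific to human albumin.

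The kidney is a target organ in the monkey studies (Section 5.3.1.3), and Section 6.4 promises special attention to renal function, with early biomarkers as a follow-up if function changes. The stored aliquots are therefore insurance: they are most likely to be run once creatinine or BUN has moved. By then, urine already mixed with the additive cannot be collected again. Section 8.2.1 of this version records that Cohort 5 has been completed, so some stored samples may already exist.

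**Working it through.** The protocol states no figure to reproduce. The check follows the sample path and then illustrates the size under stated assumptions.

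**Step 1: sample path.** Urine is collected into containers with the additive and pooled by period (13.1.2), then weighed. The biomarker aliquot is taken after weighing (13.3.2), at every scheduled time point (footnote n). On the plain wording, contact with the additive comes before the aliquot.

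**Step 2: markers exposed.** Total protein is exposed directly. Albumin is exposed only if the assay cross-reacts with bovine albumin, and no assay is named. No effect is shown for the other six markers.

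**Step 3: protein added.** The final concentration is assumed, because the protocol gives none. Since 1% w/v = 10 g/L:

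| Assumed additive (% w/v) | Protein added (g/L) |
|---|---|
| 0.01 | 0.1 |
| 0.1 | 1 |
| 1 | 10 |
| 2 | 20 |

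Against an assumed upper normal urinary protein of 0.15 g/L, the ratio is 0.1/0.15 = 0.67 at the low end, 1/0.15 = 6.7 at 0.1%, 10/0.15 = 66.7 at 1%, and 20/0.15 = 133 at the high end. Even the lowest assumed concentration is about two-thirds of that normal limit.

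**Step 4: does change from baseline remove it?** Let *m* be the additive mass per container, *V0* the pre-dose volume and *V* the pooled post-dose volume. The spurious change in total protein is *m/V − m/V0*, which is zero only when the two concentrations are equal. Assume a fixed *m* = 1 g, *V0* = 0.1 to 0.3 L and *V* = 0.5 to 2 L:

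- smallest: 1/0.5 − 1/0.3 = 2.00 − 3.33 = −1.33 g/L
- largest: 1/2 − 1/0.1 = 0.5 − 10 = −9.5 g/L

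The result scales with *m*. Its sign is negative because the pooled volumes are assumed larger than the pre-dose sample, so the artefact would tend to hide a true rise in protein.

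The schedule itself makes unequal volumes likely. Baseline is a single blank sample, while the post-dose pools cover 12 h (0–12, 12–24) or 24 h (24–48, 48–72). At constant urine flow and a fixed mass, a 24 h pool has 12/24 = half the additive concentration of a 12 h pool.

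**Step 5: does the placebo group remove it?** Placebo subjects have the same additive, so an active-versus-placebo contrast survives in principle. Each cohort has 6 active and 2 placebo subjects (Section 8.8.2), and under a fixed additive mass the volume-driven variation adds noise to that small comparison.

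**The case against.** **The containers may be the shipped tubes.** The additive sentence continues with shipment to the bioanalytical laboratory, and the preceding paragraph says that what is shipped is an aliquot, not the pool. On that reading the biomarker aliquot never meets the additive. This is a fair alternative and it stands as a possibility. But the verb is collected into, no additive-free route is described, and the reader should not have to choose.

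**The processing manual may deal with it.** It may; it is not available here. The protocol nevertheless fixes the additive, the source of the aliquot and the order relative to weighing, so the manual would have to supply a safeguard that the protocol lacks.

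**The markers are exploratory and may never be assayed.** This is correct and limits the severity. The primary endpoint's renal focus is serum creatinine, BUN and creatinine clearance (7.2.1). The renal escalation criteria use creatinine clearance and serum creatinine (8.2.1), and renal withdrawal uses creatinine clearance (8.3). Serum cystatin C is measured with the safety laboratory tests. None of these depends on urinary protein.

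**The sizes are assumed.** They are. If the additive were dosed in proportion to volume, the spurious change in Step 4 would vanish, although the constant from Step 3 would remain in every reading.

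**A stronger reading on urinalysis.** A reader might infer that dipstick protein, part of the safety laboratory set, is contaminated too. The document does not support that. Section 14.6.2 says "Any urine used for urinalysis will be added back to the full sample for PK analysis", which suggests that this urine is held apart when it is read. Of the four scheduled urinalysis time points (screening, admission, 72 h, follow-up), only 72 h falls within PK urine collection. Microscopy urine does come from the weighed collection, but nothing shows that dissolved albumin affects microscopy.

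**Conclusion.** The concern holds on the plain wording, as a moderate issue. If the protocol is followed as written, urinary total protein would be dominated by the additive at all but the lowest assumed concentrations. Albumin would be unreliable unless the assay is shown not to read bovine albumin. Change from baseline is no remedy unless the additive concentration is the same at every time point.

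This rests on reading the additive sentence as referring to the collection containers. If it refers only to the shipped PK tubes, what remains is ambiguous wording. The magnitudes (0.1 to 20 g/L added; −1.3 to −9.5 g/L spurious change per gram of additive) are illustrations under assumed concentrations and volumes.

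It would be tempting to conclude that the trial's renal safety monitoring is compromised, or that the whole biomarker panel is lost. Neither follows: the primary renal parameters and decision rules use blood-based measures, and no effect on the other six urine markers is shown.

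**What to change.** Reconcile Sections 13.1.2 and 13.3.2 and Appendix 2 footnote n:

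- State that the biomarker aliquots are taken from urine that has had no contact with bovine serum albumin. The additive then goes in after those aliquots are drawn, or only into the PK aliquot tube.
- If adsorption of the drug requires the additive at collection, set aside a weighed, additive-free portion of each void for the biomarkers. Count its weight in the total volume used for amount excreted.
- If the current text was meant to cover only the shipped PK tubes, say so in one sentence.
- For samples already collected with additive contact, treat total protein as not interpretable. Treat albumin the same way unless the assay is shown not to read bovine albumin.

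The cost is protocol and processing-manual wording, plus at most one plain container per interval. The void-by-void split would add handling work, but is needed only if adsorption demands it. The one technical downside is that adsorption of the drug to the container before the additive is added must be checked, so that urinary PK is not biased in exchange.

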#### **13.2** Assessment of Pharmacodynamics

Not applicable for this Phase I study.

#### **13.3 Exploratory Assessments**

#### 13.3.1 Holter extracted ECGs

Continuous Holter monitoring will commence at least 1 h prior to dosing until 24 h post-dose, ie, after the blood sample for PK has been withdrawn at 24 h post-dose. Subjects will be required to be supine for 20 min (10 min rest period, 10 min extraction) prior to the nominal time point where an ECG extraction is scheduled. The extraction will be taken in the 10 min immediately prior to the nominal time point and no other procedures will be performed within this time window. All ECG extractions will occur in triplicate. Values from triplicates (RR, PR, QRS, and QT) will be averaged in order to obtain one single value per time point. On Day 1, three pre-dose triplicates will be extracted and averaged to establish a baseline value.

The recordings will be archived for a maximum of 25 years and analyzed only in case the clinical development of DNDI-0690 progresses to a MAD trial, eg, the Holter extracted ECGs will be analysed together with the Holter extracted ECGs collected in the MAD trial, and reported in a separate report. Holter extraction window times will be recorded in the subject's source. The Holter data collected in this trial will not be part of the trial's clinical data base.

Where any scheduled extractions are missed a protocol deviation will be recorded, loss of leads or interruption of the recording outside of the scheduled extractions will not be considered a protocol deviation.

See Section 10.3.2 for details on timing of Holter extractions in relation to other procedures.

In case the extracted ECG data are analysed, the following analyses are planned and will be reported in a separate report:

Changes from baseline (average of the three pre-dose extracted ECG triplicates) with the extracted ECG triplicates recorded on Day 1 will be calculated for each parameter:

- Categorical analysis for RR, HR, PR, QRS, QT, QTcF, QTcB, ΔHR, ΔRR, ΔPR, ΔQRS, ΔQT, ΔQTcF and ΔQTcB according to the thresholds defined below.
- ECG morphological analysis.

The pre-defined thresholds for the categorical analysis for maximum actual values will be:

- QTc interval > 450 msec (male) / > 470 msec (female)
- QTc interval > 480 msec
- QT/QTc interval > 500 msec

and for maximum changes from baseline:

- ΔQTc interval > 30 msec
- ΔQTc interval > 60 msec

All Holter extracted ECGs parameters and their changes from baseline will be summarised by dose regimen and time-point.

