#### Number of Subjects Planned:

It is planned to enrol 8 healthy male subjects in Cohorts 1 to 7 and 8 healthy WONCBP subjects in Cohort 8 (8 planned cohorts, 64 subjects in total). This will ensure data in 6 evaluable subjects per cohort. Subjects withdrawn due to an IMP-related adverse event (AE) will not be replaced. Subjects who are withdrawn for other reasons may be replaced as required by agreement between the PI and Sponsor to ensure sufficient evaluable subjects. Up to 2 additional subjects per cohort may be enrolled into the study. The maximum number of subjects that may be dosed is 80. An evaluable subject is defined as a subject who has sufficient PK and safety data up to 72 h post-dose or was withdrawn prior to 72 h due to an adverse event.

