#### 7.1.3 Exploratory Objectives

- To investigate any potential changes to renal toxicity markers in plasma and urine.
- To investigate the metabolite profile of DNDI-0690.
- To assess the effect of DNDI-0690 on Holter ECG parameters.
- To investigate the PK of DNDI-0690 after singles doses in the fed versus fasted state in healthy male subjects
- To investigate the PK of DNDI-0690 after single doses in healthy WONCBP versus healthy male subjects

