#### 10.3.2 Timing of Procedures

There are times where the protocol requires more than one procedure to be completed at the same time point. In these instances the following will apply to post-dose time points:

PK samples should take priority over other procedures scheduled at the same time point.

As guidance, where Holter extracted ECGs coincide with other procedures ie. vital signs and ECGs the order of procedures will be:

ECGs should be taken prior to vital signs when both measurements are scheduled at the same time point. Holter extracted ECGs will be taken in the 10 min immediately prior to the nominal PK time point and no other procedures will be performed within this time window. Where required, procedures may be performed in the rest period prior to extractions. Other assessments, eg physical examinations etc, will be performed within the required time windows.

All safety assessments will be timed and performed relative to the start of dosing.

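### The planned Holter analysis contains no placebo-corrected or concentration-based QTc estimate, although the matched data for one are collected

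*Protocol*

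**What the plan says.** The exploratory objective in section 7.1.3 is "To assess the effect of DNDI-0690 on Holter ECG parameters". Section 13.3.1 states the analyses planned if the recordings are analysed:

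- "Categorical analysis for RR, HR, PR, QRS, QT, QTcF, QTcB" and the corresponding changes from baseline, against fixed thresholds. The lowest change threshold is "ΔQTc interval > 30 msec"; the other is 60 ms. They apply to maximum changes.
- "ECG morphological analysis".
- "All Holter extracted ECGs parameters and their changes from baseline will be summarised by dose regimen and time-point".

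The same section makes the analysis conditional. The recordings are archived outside the trial's clinical database. They are analysed only if a MAD trial follows, together with that trial's Holter ECGs and in a separate report. Section 15.4 confirms that they are not analysed within this study for now.

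On data collection, section 10.3.2 says "Holter extracted ECGs will be taken in the 10 min immediately prior to the nominal PK time point". Appendix 2 gives the extraction times as "pre-dose and 0.5, 1, 1.5, 2, 2.5, 3, 4, 6, 9, 12 and 24 h post-dose", and every one of them is also a plasma sampling time. Extractions are triplicate, and baseline averages three pre-dose triplicates. The synopsis plans "8 planned cohorts, 64 subjects in total", and section 8.8.2 allocates 3:1.

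**The concern.** Assessing a drug effect needs a comparator and a measure of uncertainty, and the stated plan has neither. Section 15.4 names a combined placebo group for the safety summaries. Section 13.3.1 names none for Holter, and in Table 1 each of Regimens A to H covers both active and placebo capsules. Changes from baseline without placebo correction mix any drug effect with time of day and meals: lunch at about 4 h in all cohorts, and in Cohort 7 a high-fat breakfast begun 30 min before dosing. Threshold counts pick up large individual changes but say little about a small shift in the mean.

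The design already carries the burden that a concentration-QTc analysis requires: triplicates, matched sampling, a careful baseline and concurrent placebo. What is at stake is a usable bound on the QTc effect for the combined single- and multiple-dose report.

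**Working it through.** **Step 1. The plan's own numbers.** 8 cohorts × 8 = 64 subjects; with up to 2 replacements per cohort, 64 + 16 = 80, as stated. Each cohort has 1 + 5 = 6 active and 1 + 1 = 2 placebo subjects, so 48 active and 16 placebo overall. With 11 post-dose times there are 64 × 11 = 704 planned ECG-plasma pairs, 528 of them on active drug. The protocol gives no QTc standard deviation, margin or precision target, so every SD below is an assumption.

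**Step 2. Threshold counts.** The one-sided 95% upper limit after zero events is 1 − 0.05^(1/n).

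- 0 of 6: 1 − 0.05^(1/6) = 39.3%.
- 0 of 48, all active doses together: 1 − 0.05^(1/48) = 6.1%.

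Now suppose a true mean shift of 10 ms at one time point. For one subject, q = 1 − Φ((30 − 10)/SD); for any of six, P = 1 − (1 − q)^6.

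| Assumed SD (ms) | q | P(any of 6 above 30 ms) |
|---|---|---|
| 6 | 0.0004 | 0.3% |
| 8 | 0.0062 | 3.7% |
| 10 | 0.0228 | 12.9% |
| 12 | 0.0478 | 25.5% |

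The protocol applies its thresholds to the maximum over time, which raises these chances. A simulation over the 11 times, with a 10 ms peak effect, equal exposure in all subjects and between/within-subject SDs of 4/5, 5/6 and 7/7 ms (total 6.4 to 9.9 ms), gives about 2%, 14% and 44%.

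**Step 3. One cohort against placebo at one time.** The 90% CI half-width is t(0.95, n1 + n2 − 2) × SD × √(1/n1 + 1/n2). For 6 v 16 the factors are 1.725 and 0.479; for 6 v 2 they are 1.943 and 0.816.

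| Assumed SD (ms) | 6 v 16 pooled placebo (ms) | 6 v own 2 placebo (ms) |
|---|---|---|
| 6 | 5.0 | 9.5 |
| 8 | 6.6 | 12.7 |
| 10 | 8.3 | 15.9 |
| 12 | 9.9 | 19.0 |

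**Step 4. Concentration-QTc model.** The model is change in QTcF = time effect + treatment + slope × concentration + subject effect + error. The quantity of interest is treatment + slope × Cmax at the top dose, with its variance from generalised least squares and a multiplier of t(0.95, 60).

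- From the protocol: 48 active and 16 placebo subjects, 11 times, a half-life of 7.4 h (section 6.1), and Cmax of 0.0958/10 = 0.00958 µg/mL per mg (Table 2).
- Assumed: doses of 10, 50, 150, 300, 600, 900, 300 and 600 mg; absorption rate 1 per hour; exposure CV 30%; between/within SDs of 4/4.5, 5/6.2, 6/8 and 7/9.7 ms; independent errors.

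For total SD 6, 8, 10 and 12 ms the half-widths are about 2.6, 3.3, 4.1 and 4.9 ms. With sub-proportional exposure (Cmax to the power 0.6) they are about 2.5, 3.2, 3.8 and 4.6 ms.

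Under strict proportionality, 900 mg would give 900 × 0.00958 = 8.6 µg/mL, just above the 8.0 µg/mL limit in section 8.2.1, so the dose set is only illustrative. A narrower set (10, 50, 100, 200, 300, 300, 100 and 300 mg) gives 2.3 to 4.2 ms with proportional exposure, so the gain does not depend on an extreme top dose.

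**Step 5. What a simple contrast could do.** Take six active subjects against the 12 placebo subjects of the six fasted male cohorts. The factors are 1.746 and √(1/6 + 1/12) = 0.5, so the half-width is 1.746 × 0.5 × SD: 5.6 ms at SD 6.4 and 8.6 ms at SD 9.9. With no true effect, the noncentral t distribution gives a chance of about 90% and 60% respectively that the upper limit lies below 10 ms at a given time.

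**The case against.** The strongest objection is that this is a conditional, exploratory analysis for another report. Model form, covariates and interval level normally belong in that report's analysis plan, and section 13.3.1 does not call its list exhaustive. That limits the weight of the point but does not remove it: the section says which analyses are planned, and neither a contrast with placebo nor a model is among them.

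A reader might infer that the Holter data go unused. The documents do not support that. The recordings are archived for analysis with the MAD data, and a model can still be added.

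A reader might also infer that the plan could not tell no effect from one of about 10 ms. That is too strong as well. Means and SDs by dose and time would let someone form a contrast with placebo, and step 5 shows that it would often exclude 10 ms. Placebo is probably not absent from the tables either: section 15.4 describes the safety ECG summaries by dose regimen while also combining all placebo subjects. What stands is that no contrast or interval is planned and no placebo group is named for Holter.

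Finally, the precision figures rest on assumed SDs and doses. Only Cohort 1's dose is fixed, doses may be repeated or reduced, and exposure may reach a plateau.

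**Conclusion.** The point holds as a weakness in a stated, conditional, exploratory analysis. Section 13.3.1 fixes a less informative method than its own data allow. The 39% upper limit for 0 of 6 needs no SD assumption. The comparison of about 5 to 10 ms for one cohort against pooled placebo at one time, and about 2.5 to 5 ms for the model, assumes an SD of 6 to 12 ms, the illustrative doses and exposure profile, and a linear relation without delay. Across these settings the half-width is roughly halved; the absolute values are only indicative.

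The point should not be read as a gap in subject protection. In-study cardiac monitoring rests on the safety ECGs, the QTcF rules in sections 8.2.1 and 8.3 and Troponin I, not on the Holter data.

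**What to change.** In section 13.3.1, add as the main analysis of the separate Holter report a linear mixed model of change in QTcF on time-matched plasma concentration:

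- Include all active and pooled placebo subjects, with placebo concentration set to 0.
- Use treatment and time point as fixed factors, centred baseline QTcF as covariate and a subject random effect. Add a study term when MAD data are pooled.
- Report the placebo-corrected effect with a two-sided 90% CI at the geometric mean Cmax of each dose.
- Treat fed Cohort 7 as a sensitivity subset by repeating the fit without it.
- Check linearity and delay with plots of concentration and QTcF change.
- Keep the categorical and morphology outputs as supportive.
- State that Holter extraction times will stay linkable to PK results and treatment codes, since the recordings sit outside the clinical database.

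The cost is protocol or analysis-plan wording and modest programming; no subjects, ECGs or samples are added. The downside is reliance on linearity and absence of delay, which the plots can challenge but not prove.
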